Version Date: 3/2/2018

Principal Investigator: [name]

Co-Investigator: [name]

Study Physician: [name]

Study Title: Body Fat Reducing Effect and Safety of Enzymatically Modified Isoquercitrin in Overweight and Obese Subjects

I. Aim and Hypotheses

Specific Aim 1: To compare the body fat reducing effect of 360mg/day enzymatically modified isoquercitrin (EMIQ) with that of a placebo.

Hypothesis 1: Compared to a placebo, participants receiving EMIQ supplementation will have a greater reduction in total body fat as evidenced by measures of whole body DXA scan, skinfold thickness, waist to hip circumference ratio, resting metabolic rate, plasma adiponectin levels, physical activity, and dietary intake.

Specific Aim 2: To determine the safety of long term intake of EMIQ.

Hypothesis 2: Long-term intake of EMIQ has no ill effect on participant health as evidenced by measures of heart, liver, kidney function, and psychological state.

II. Background and Rationale

Dietary quercetin is a natural bioactive polyphenol with potential health benefits and the capacity to prevent development of various diseases including those of the cardiovascular system, central nervous system and others [1-3]. It is widely distributed in various plant foods such as onions, broccoli, concord grapes, apples and more [4]. In plants, quercetin is present as conjugated with different forms of glucosides [5], which affect their bioavailability. The bioavailability of different forms of quercetin has been the subject of several investigations [6]. Enzymatically-modified isoquercitrin (EMIQ) is a mixture of quercetin monoglucoside and its α -oligoglucosides, which mainly consist of quercetin-3-O- β -glucoside (Q3G) and α -glucosyl derivatives with 1-7 of additional linear glucose moieties [7, 8]. Supplementing the diet of apoE-deficient mice with EMIQ increased quercetin levels and suppressed atherogenesis in this mouse model of human atherosclerosis[9]. In human trials, the bioavailability of EMIQ

has been shown to be 17-fold higher than quercetin aglycone [10]. After efficient absorption of EMIQ, quercetin is released, and it exerts its biological activity such as reducing body fat, improving cardiovascular health and reducing blood pressure.

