EMIQ has been shown to be effective in reducing body fat in Japanese people who have different dietary habits and lifestyle from that of a person in the United States. Thus, this study is designed to investigate if EMIQ is also effective in reducing body fat in subjects with a western lifestyle.

Quercetin, according to Seo et al [11] in addition to being a very strong antioxidant, prevents adipogenesis by regulating two sets of enzymes, a) by upregulating adipose triglyceride lipase (ATGL) and hormone sensitive lipase (HSL) expression and, b) by downregulating fatty acid synthesis (FAS), lipoprotein lipase (LPL) and adipocyte fatty acid-binding protein (aP2) expression, through expression of transcription factors such as C/EBP α , PPAR γ , SREBP-1. These observations suggest that quercetin has therapeutic potential for body fat reduction through regulating the expression of transcriptional factors and enzymes associated with adipogenesis. Dong et al [12] also reported that dietary quercetin reduces high fat diet-induced body weight gain, fat deposition, and insulin resistance and suppresses glucose uptake by adipose tissue. They reported that these effects of dietary quercetin is mediated through quercetin activating of AMPK/ACC signaling pathway which promotes fatty acid β -oxidation and suppresses fatty acid esterification into triglyceride in adipocyte. Administration of 275 mg/d for 12 weeks reduced total body fat, visceral fat and subcutaneous fat in Japanese subjects. EMIQ is classified by the Food and Drug Administration (FDA) as Generally Recognized As Safe (**GRAS**). Thus, it should be considered a safe compound in order to investigate its potential biological activities in humans.

III. Research Plan

A. Experimental Design

This is a randomized, double-blind, placebo controlled study.

B. Sample Size and Statistical Analyses

50 subjects will be required to complete this 12 week study (though 150 will be screened and 64 will be enrolled to ensure completion of 50 subjects). Subjects will be randomized 1:1 into either the treatment (EMIQ) or placebo group. The study physician, [name], will hold the code to the randomization which will be revealed upon completion of the study or if adverse event occurs.

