To calculate number of subjects needed per group and provide 80% power at $\alpha=0.05$ we used mean differences and standard deviation (EMIQ: 19 ± 24.62 and Placebo: 1 ± 12.87) of whole abdominal fat loss from an early published study conducted in Japan, where the Japanese volunteers consumed 275mg EMIQ per day for 12 weeks and showed a positive impact of EMIQ on reduction of fat depots. We plugged in data from that study into this formula $N=1+[16(xS^2/d^2)]$ to calculate sample size. Using this formula the number of subjects in each group were calculated to be $n=18$. However, we selected to use 25 subjects per group which increases power of study to $>85\%$. 25 subjects per group is a conservative sample size, which make us to expect a larger difference in the means with a higher dose of EMIQ intake.

The primary objective of this study is to demonstrate reduction of total body fat following 12 weeks of EMIQ intervention. Therefore, we will determine statistically if EMIQ is effective to reduce percent body weight, total abdominal fat, subcutaneous and visceral fat after 12 weeks of intervention compared to baseline values. We plan to compare the two group medians with the Mann-Whitney U test. After reviewing the data at the completion of the study, we can assume normality, then we will compare the two group means with parametric t-test.

C. Subject Characteristics

Inclusion Criteria:

- Male or female age 18-65 years.
- Premenopausal female with regular menstrual cycle or post-menopausal female with cessation of menstrual cycle for a minimum of 6 months.
- BMI in the range of 26.0-37.0_
- Beck Depression Inventory Score less than 20.
- Fluency in spoken or written English.
- Willingness to be randomized to take EMIQ or placebo.
- Must weigh at least 164lbs

Exclusion Criteria:

- Any major illness or condition that may interfere with study outcomes at the discretion of the study physician.
- Diabetes Type I & Type II, or use of any pharmacological treatment for diabetes.
- Use of medications that interfere with energy metabolism
- Receiving hormone therapy growth hormone, testosterone, or estrogen with the exception of hormone contraceptives.
- GI diseases, conditions or medications known to influence GI absorption including active peptic ulcer disease or inflammatory bowel disease such as

- ulcerative colitis, Crohn's disease, celiac disease, chronic diarrhea or constipation.
- Undergone gastric bypass or other bariatric weight loss procedure.

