using an indirect calorimeter calibrated using test gases of known concentration. Subjects will be instructed to relax and avoid fidgeting and sleeping during the measurements. Measures will be made under thermo-neutral conditions for 40 minutes. Rates of energy expenditure will be calculated from VO_2 and VCO_2 using Weir's equation. Fasting oral temperature will be measured on days in which RMR is measured.

Dual-Energy X-Ray Absorptiometry (DXA):

DXA measurement will be performed only at the visits 2 and 5. Once subjects have completed measures at the HNRCA, they will be escorted to the Body Composition Analysis Center. The subject should be asked about and examined for metal that could be in the scan path. Typical items to look for are earrings, eyeglasses, wristwatches, coins, rings, buttons, buckles, zippers, and support braces. The subject must remove shoes, and it may be necessary to remove skirts, slacks, brassieres, etc. If clothes are removed, a medical cotton gown will be provided during the scan. Subjects will be asked to lie down on the scan table without allowing their hands and legs to overlap while the scan is performed. The analysis of each whole body scan will generate values for total body lean, total BMC, total body fat, total body mass, trunk fat, trunk lean, total bone mineral density (BMD), lumbar BMD, upper extremity fat, upper extremity lean, lower extremity fat and lower extremity lean. To minimize error, each patient will be scanned on the same machine from baseline to final. Scans will be analyzed by the Body Composition Analysis Lab.

Electrocardiogram (EKG):

An EKG will be performed by MRU staff at visits 2 and 3. Areas of participant's chest, arms and legs will be rubbed with alcohol and 12 electrodes will be attached to the skin. Participants will be required to lie still on their backs in bed while electrical activity is recorded by these electrodes. Electrodes will be removed after the test, which takes approximately 20 minutes to administer.

Skinfold Thickness:

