- [name] will regularly monitor potential risks and procedures in order to protect participants from risk.
- Will discuss any adverse events with the study physician on a weekly basis.
- Will report any adverse events associated with participation in the study protocol and file all required annual paperwork with the IRB.
- Will evaluate the progress of the study including periodic assessments of data quality and timeliness, recruitment, enrollment and retention, protocol violations, unanticipated events, volunteer risk vs. benefit, and anything else that may have an impact on the study outcome.
- Maintain vigilance of developments outside of the study that could affect participant's safety.
- Perform, at minimum, two reviews of the data per year to ensure safety and efficacy of the study.
- Responsibility for all procedures performed.
- Reviews all data as it may relate to volunteer safety. This includes factors like participant retention and reason for drop-out.
- Reporting all serious adverse events regardless of their relation to the study protocol.
- Provide the IRB with summaries of all adverse events.
- At the discretion of [name], the Co-I, [name], or [name], the study may be terminated at any time if the risks to study subjects are found to outweigh the potential benefits.

Additionally, no personal results will be communicated to study participants. However, participants will be informed of any necessary new findings developed during the course of this research study. Written results may be given directly, or mailed, to participants if they are still in the study, or mailed to them if they have completed their participation in the study.

H. Outcome

Our goal is to assess the safety and efficacy of EMIQ as it relates to body fat reduction. We predict that there will be no changes in health, and that there will be a significant difference between change in total body fat between the treatment and placebo groups.

I. Tissue Banking Considerations

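### The stated power of more than 85% is for whole abdominal fat, but the primary objective is total body fat; the number to be randomised is also given inconsistently (64 or 50)

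*Protocol*

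**What the plan says.** Section III.B of the protocol sizes the trial from an earlier Japanese study of 275 mg/day, using "EMIQ: 19 ± 24.62 and Placebo: 1 ± 12.87) of whole abdominal fat loss". The target is 80% power at alpha 0.05. The formula N = 1 + 16 S²/d² is reported to give 18 per group. The protocol then says "we selected to use 25 subjects per group which increases power of study to" more than 85%.

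The next paragraph of III.B reads "The primary objective of this study is to demonstrate reduction of total body fat following 12 weeks of EMIQ intervention", and continues "we will determine statistically if EMIQ is effective to reduce percent body weight, total abdominal fat, subcutaneous and visceral fat". Total body fat is not in that list.

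Elsewhere total body fat is plainly the target. Hypothesis 1 (section I) predicts that "participants receiving EMIQ supplementation will have a greater reduction in total body fat". Section III.H predicts that "there will be a significant difference between change in total body fat between the treatment and placebo groups". On prior evidence, section II says only "Administration of 275 mg/d for 12 weeks reduced total body fat, visceral fat and subcutaneous fat in Japanese subjects", without figures.

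On numbers, III.B enrols 64 so that 50 complete. The Overview in III.E randomly assigns 50 in total, 25 to each group, and later says that 50 will be recruited and admitted, with those volunteers scheduled from visit 1 onwards. The SAP analyses subjects who completed the study. It names no primary variable and gives no sample-size basis.

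**The concern.** The power figure is presented as belonging to the study, but it was calculated for one outcome while the stated objective is another. The two fat measures are probably correlated. Even so, nothing in the documents shows that the standardised effect seen for abdominal fat carries over to total body fat. A null result on total body fat would be read against a power that was never calculated for it. The list in III.B adds to the doubt, since it includes total abdominal fat and omits total body fat.

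The second issue is that 50 is the number completing in III.B but the number randomised or admitted in III.E. The protocol removes subjects after supplementation starts, for low compliance or missed visits (III.C) and for visits outside the window (III.E, Compliance). With a completers-only analysis, the number randomised decides how much of this loss the trial can absorb.

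**Working it through.** **Inputs.** All come from protocol III.B: means 19 and 1, so d = 18; SDs 24.62 and 12.87; alpha 0.05, taken as two-sided (sidedness is not stated, but the constant 16 fits two-sided 0.05 with 80% power); 1:1 allocation; 25 per group; 64 enrolled for 50 completers.

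**1. Reproducing the plan's figures (abdominal fat).**

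- Pooled SD = √[(24.62² + 12.87²)/2] = √385.89 = 19.64. Standardised effect = 18/19.64 = 0.916.
- Power at 25 per group, noncentral t: 88.8%. The claim of more than 85% is correct for this outcome.
- Mann-Whitney, which III.B plans first and the SAP keeps as a fallback, simulated with normal data and the two stated SDs: about 86%.
- n = 18: S is not defined. Averaging the SDs gives (24.62 + 12.87)/2 = 18.745, and 1 + 16 × 18.745²/18² = 18.35, which matches. The pooled variance gives 1 + 16 × 385.89/324 = 20.06. At 18 per group, t-test power is 76.1% with the pooled SD and 79.9% with the averaged SD. This does not affect the 25 chosen.

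**2. Total body fat.** With no difference or SD in the documents, power cannot be calculated. What can be stated is the effect that 25 completers per arm would detect (two-sided t-test, 48 df):

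| True effect (SD units) | Power |
|---|---|
| 0.5 (assumed) | 41% |
| 0.7 (assumed) | 68% |
| 0.809 | 80% |
| 0.865 | 85% |
| 0.9 (assumed) | 88% |

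**3. Number randomised.** Loss implied by III.B: 14/64 = 21.9%. Also 32 × 50/64 = 25, so 64 enrolled is consistent with 25 completers per arm. Power for abdominal fat as completers fall (pooled SD):

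| Completers per arm | t-test | Mann-Whitney (simulated) |
|---|---|---|
| 25/25 | 88.8% | about 86% |
| 24/24 | 87.4% | just below 85% |
| 23/23 | 86.0% | – |
| 22/23 | 85.2% | – |
| 22/22 | 84% | – |
| 20/20 | 80.6% | about 77% |
| 19/20 | 79.5% | about 76% |

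The 19/20 row applies the implied 21.9% loss to 50 randomised (50 × 50/64 = 39.1). No document plans that combination. With the averaged SD the t-test figures are higher: 91.4% at 25/25, 84.1% at 20/20 and 83.1% at 19/20.

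**The case against.** There is no arithmetic error at 25 per group, and III.B names the sizing variable in the same paragraph as the power, so a careful reader can see what it refers to. Percent body weight, the first item in the test list, may be a slip for percent body fat. The intention to test total body fat is clear from sections I and III.H, and DXA measures it at visits 2 and 5. The 41% to 88% range holds for any trial with 25 per arm, so it shows a missing input and not an underpowered trial. On numbers, the 50 in III.E may simply repeat the completer target, and some of the 14 may leave before randomised capsules are dispensed at visit 2.

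Much of this is fair. The figure is right for its own outcome, total body fat is documented as the target, and the loss of a few subjects costs little power by t-test. The mismatch remains, however. The figure is called the power of the study and no input for the stated objective is given. A slip in the list would itself need correcting. The Overview says that 50 are randomly assigned and schedules the 50 admitted volunteers from visit 1, which cannot be squared with 64 enrolled.

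**Conclusion.** The concern holds. The figure of more than 85% is correct for whole abdominal fat with 25 completers per arm (88.8% by t-test, about 86% by Mann-Whitney), but it is not the power for the primary objective. That power is unknown. Reaching 85% would need a true effect on total body fat of at least 0.865 SD, and 80% would need 0.81 SD. This assumes a two-sided test, normal data and 25 completers per arm.

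The conflict over 64 and 50 is real but has a smaller consequence. If only 50 were randomised, more than 85% for abdominal fat would survive up to five losses, evenly split, by t-test, and the 80% target would hold down to 20 per arm. By Mann-Whitney the margin is thinner, and power is already just below 85% at 24 per arm. These are points that should be corrected; they do not show that the trial is underpowered.

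**What to change.** In III.B, replace the power sentence with text to this effect: with 25 completers per group, power is about 89% (two-sided t-test; about 86% by Mann-Whitney) for whole abdominal fat loss, assuming a difference of 18 and a pooled SD of 19.64; for change in total body fat, the primary objective, 25 completers per group detect 0.81 SD with 80% power and 0.865 SD with 85%. If the sponsor has a source for a total body fat difference and SD, add them.

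Add total body fat to the tested variables in III.B, and clarify whether percent body weight is meant.

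State one number randomised and use it in III.B and in both places in the III.E Overview, described as chosen to leave 25 completers per arm. That is 64 (32 per arm) if the implied loss falls after randomisation, and fewer if part of it falls before.

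Define S in the formula. With the pooled variance the formula gives 20.06, and an exact t-test calculation gives 20 per group for 80% power.

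The cost is wording. Total body fat is already a DXA output (III.F: "The analysis of each whole body scan will generate values for total body lean, total BMC, total body fat"), so no new measurement is needed. No one beyond the 64 is enrolled, though up to 14 more would be randomised than III.E describes. A total body fat SD would have to come from outside these documents.
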